2.2.3 ASSESSMENT OF POTENTIAL RISKS AND BENEFITS

Evidence supports accuracy and reliability of diagnosis by asynchronous teledermatology. Furthermore, multiple studies have demonstrated concordance in management plans between care delivered through asynchronous teledermatology versus in person. However, potential risks remain with either arm of the study with regards to adverse events related to AD exacerbation or adverse events arising from AD treatment. Because the study is pragmatic in design, it enables in-person or online visits at frequencies that are individualized and deemed medically necessary by the provider. Thus, providers and patients in both arms can follow up at frequencies that are necessary to manage AD and any treatment-related adverse events. Thus, we deem the probability of experiencing untoward events beyond what would otherwise be expected via routine care for this population to be low.

Protection against Adverse Events during Management of Atopic Dermatitis

To mitigate risks of adverse events related to AD or the treatment, the PI and the study staff will continuously monitor patients for adverse events. Patients can report adverse events using two methods: (1) using the "Adverse Event Collection Form", which is captured at quarterly intervals, or (2) reporting AEs spontaneously to the study at any time 24/7. The study team or the patient's provider will address adverse events as they occur.

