5.4.2 RETENTION PLAN

Prior to study initiation, we will conduct pre-trial retention training for the study staff. Prior to enrollment, the study staff will communicate with eligible patients regarding the importance of completing all outcome assessments. We will emphasize the importance of full participation during screening, enrollment, and throughout the trial.

It is important to note that, for online and in-person visits between the provider and patients, these visits occur at an individualized frequency based on medical necessity. However, the collection of outcome assessments (disease-severity, quality-of-life endpoints, and selected access-to-care measures) occurs at a quarterly basis for all participants.

All subjects will be reminded via email, text, or telephone to submit their quarterly outcome assessments beginning 7 days prior to the due date. If a subject fails to submit the quarterly outcome assessments within 2 days of the due date, the subject will be contacted using telephone and/or electronic methods to remind them to submit the assessments. The study staff will also discuss with the participant strategies to improve adherence with the study requirements. If the participant cannot be contacted after at least five attempts, a certified return receipt letter will be sent to encourage continuation in the trial.

If a participant fails to complete a quarterly assessment within 21 days of the due date, the study staff will make at least five attempts to contact (at least three telephone calls, two emails, and, if necessary, a certified return receipt letter to the participant's last known mailing address or local equivalent method). These contact attempts will be documented in the participant's study file.

If a participant wishes to withdraw from the study, the study coordinators will attempt to collect the Month 12 visit data as well as detailed data on the reasons for the discontinuation from the study. The study coordinators are encouraged to share their ideas and experiences to promote participant retention via regular communication during staff meetings.

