6.1.1.1 WHAT DEFINES AN ONLINE VISIT?

In the TCH model, online communication is classified as either "online visits" or "follow-up questions." An online visit contains photos of appropriate quality, history of present illness, medications, allergies, review of systems, and a provider's assessment and plan.

In contrast, a follow-up question refers to an *ad hoc* question from a patient that is submitted within 30 days following a prior online visit.

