The hypothesis for access-to-care measures is that TCH provides *superior* access to specialist care than in- person model. For these analyses, access-to-care measures include transportation and time needed for evaluation.

Linear regression models will be used to test whether there is a difference between the groups.

Analysis of Costs (Aim 3)

Cost analysis in healthcare research is essential for evaluating the financial impact of different treatment models on both patients and healthcare systems.²⁶⁻²⁷ For this aim, out-of-pocket (OOP) costs represent a significant factor in determining the feasibility and accessibility of team-based connected health (TCH) compared to traditional in-person care for atopic dermatitis (AD). By analyzing OOP expenditures, this study will provide insights into whether TCH offers a cost-effective alternative while maintaining equivalent clinical outcomes.³¹⁻³⁸

Healthcare utilization will be analyzed using the Cornell Services Index (CSI), which quantifies visit frequency, duration, and associated costs for medical, psychological, and professional consultations.³⁰ CSI data will be collected at baseline and again at 12 months, with ITT analysis requiring baseline values to be duplicated for patients missing follow-up data. Visit counts for different service categories will be analyzed through linear models, with treatment status as the primary predictor. Mean visit duration per patient and visit type will be compared across the two groups using Welch's two-sample t-tests and linear regression models incorporating total visit count as a covariate. The impact of TCH on visit duration will be further assessed using analysis of variance (ANOVA) models to determine potential treatment group differences. Additionally, sub-analyses will be conducted to explore whether utilization patterns differ by age or baseline disease severity. Given the pragmatic design of the study, an emphasis will be placed on real-world applicability, ensuring that findings account for the variability seen in routine clinical settings.

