Out-of-pocket (OOP) costs will be evaluated using a combination of t-tests, ANOVA, least squares regression, and random-effects gamma regression. Initial analyses will compare total OOP costs per visit and overall OOP costs between the two treatment groups using simple t-tests. Subsequently, multiple linear regression models will be used to assess the impact of TCH on total OOP costs while adjusting for relevant covariates such as treatment site, age, sex, baseline EASI score, and history of asthma. A sensitivity analysis will be performed using gamma regression models. Given that cost data often exhibit a skewed distribution, appropriate transformations or robust estimation methods will be applied where necessary to improve model fit and interpretability.³² Statistical significance for all analyses will be set at p<0.05, and all statistical computations will be conducted using standard statistical software such as R.

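### One of the three planned visit-duration analyses adjusts for total visit count, which the intervention can change, so its treatment coefficient can be biased

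*Combined protocol and SAP*

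**What the plan says.** All of this is in section 9.3.3 (Analysis of Costs, Aim 3) unless another section is named.

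- **Visit duration, first two methods:** "Mean visit duration per patient and visit type will be compared across the two groups using Welch's two-sample t-tests and linear regression models". The regression half is specified as "linear regression models incorporating total visit count as a covariate".
- **Visit duration, third method:** "The impact of TCH on visit duration will be further assessed using analysis of variance (ANOVA) models". No visit-count covariate is stated here or for the Welch test.
- **Visit count as an outcome:** the preceding sentence reads "Visit counts for different service categories will be analyzed through linear models, with treatment status as the primary predictor".
- **Out-of-pocket (OOP) cost:** "Initial analyses will compare total OOP costs per visit and overall OOP costs between the two treatment groups using simple t-tests". A regression of total OOP cost follows. The covariates it gives as examples are site, age, sex, baseline EASI and asthma history; visit count is not among them.
- **Visit frequency is not fixed:** section 2.2.3 says of the design that "it enables in-person or online visits at frequencies that are individualized and deemed medically necessary by the provider". Section 5.4.2 says that "these visits occur at an individualized frequency based on medical necessity", and section 6.1.1.2 leaves online follow-up frequency to dermatologist and patient.
- **Timing:** the CSI is completed at baseline and month 12 (Schedule of Activities) and covers the previous three months (section 8.1).

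The plan does not say whether the covariate is the baseline or the month-12 count, which duration analysis is the main one, or how patients with no visits enter a per-visit average.

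**The concern.** The same quantity is a treatment outcome in one sentence and an adjustment covariate in the next. A month-12 count reflects what happened after allocation, and TCH is designed to change how patients reach a dermatologist. There is also a route by definition: section 6.1.1.1 classes an ad hoc question "submitted within 30 days following a prior online visit" as something other than an online visit, so part of the online contact may not be counted as visits.

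Once a regression compares patients with equal counts, it no longer compares the randomised groups. Suppose that sicker patients have both more and longer visits, and that TCH raises the count. A TCH patient with a given count is then, on average, less sick than an in-person patient with that count. The arm coefficient picks up this severity difference and reports it as an effect on duration.

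At stake is the reading of one secondary utilisation result. The regression could show shorter or longer visits under TCH where there is no effect. The Welch test and ANOVA could disagree with it, all at p<0.05, with no rule for which result stands.

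**Working it through.** The documents give no effect size, SD or expected count for visit duration, so there is no planned figure to reproduce. The check asks how large the distortion could be under stated assumptions.

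**Step 1. Inputs.** From the documents: 300 patients, 1:1, 15% attrition, so 300 × 0.85 / 2 = 127.5, taken as 127 per arm; significance at p<0.05, assumed two-sided because the plan does not say. Assumed: count N and mean duration D each have SD 1 within arm; latent severity U loads b on both; treatment T shifts the count by s SD; the true effect on duration is zero.

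**Step 2. Bias.** With N = sT + bU + e and D = bU + e′, the within-arm covariance of N and D is b², which is also the slope of D on N. The adjusted arm coefficient is therefore

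0 − b² × s = −s·b².

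**Step 3. False-positive rate.** The residual variance is 1 − b⁴, and the arm-count correlation inflates the variance by 1 + s²/4. So

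SE = √[(1 − b⁴)(1 + s²/4) × 2/127].

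For b = 0.5 and s = 0.8: SE = √(0.9375 × 1.16 × 0.01575) = 0.131; −0.200/0.131 = −1.53; the rejection rate is about Φ(−1.96 + 1.53) = 33%.

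| b | s | Bias (SD) | SE | False positives |
|---|---|---|---|---|
| 0.3 | 0.3 | −0.027 | 0.126 | 5.5% |
| 0.3 | 0.5 | −0.045 | 0.129 | 6.4% |
| 0.3 | 0.8 | −0.072 | 0.135 | 8.3% |
| 0.5 | 0.3 | −0.075 | 0.123 | 9.4% |
| 0.5 | 0.5 | −0.125 | 0.125 | 17.0% |
| 0.5 | 0.8 | −0.200 | 0.131 | 33.3% |

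Simulation of the same model (6,000 trials) gave 5.4 to 8.8% at b = 0.3 and 9.0 to 33.0% at b = 0.5. The unadjusted comparison stayed at about 5%. At b = 0.2 the adjusted rate is 5.2 to 6.0%; at b = 0.5 with s = 0.1 it is about 6%. At s = 0 the bias is zero. If TCH lowers the count, the sign reverses.

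**Step 4. A second model, in minutes.** Assumptions: 4 visits on average in the control arm, Poisson counts, severity raising the log visit rate by 0.4 per SD, residual SD 8 minutes, true effect zero, 200,000 patients per scenario, and patients without visits excluded.

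| TCH/in-person visit-rate ratio | Adjusted, severity adds 3 min/SD | Adjusted, severity adds 5 min/SD |
|---|---|---|
| 0.5 | +1.6 | +2.7 |
| 0.75 | +0.8 | +1.3 |
| 1.0 | 0.0 | 0.0 |
| 1.5 | −1.3 | −2.2 |
| 2.0 | −2.4 | −3.8 |

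Without the covariate, estimates at ratios 0.75 to 1.5 lay between −0.14 and +0.16 minutes. With severity unrelated to duration, the adjusted estimate was also about zero. When the count itself changed duration (−0.5 minutes per visit, 3 min/SD, ratio 1.5), the total effect was −1.02, the direct effect 0 and the adjusted estimate −1.26: it matched neither.

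**Step 5. Zero visits.** A patient without visits has no mean duration and no cost per visit. In the second model, excluding such patients moved even the unadjusted duration difference by 0.2 to 0.4 minutes at a rate ratio of 0.5. Cost per visit itself was not simulated.

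**The case against.** The strongest reply is that the problem may not exist. The covariate could be the baseline count, which would be a legitimate adjustment. This stands as an ambiguity that the plan has to resolve. Month 12 is the more natural reading, since the regression sits beside the analysis of visit counts as an outcome.

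Second, bias needs two things that the documents do not quantify: an arm effect on count, and a shared cause of count and duration. That also stands, and the result is sensitive to it, because bias falls with the square of the severity loading. The CSI spans psychiatric, medical, support and intensive services, whereas TCH acts on atopic dermatitis care, so a shift of 0.8 SD in an all-service total may be too large.

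Third, visit duration is not itself a listed endpoint; sections 1.1 and 3 name only utilisation and costs. This limits the weight of the point but does not remove it, since utilisation is a listed Aim 3 endpoint and no duration analysis is given precedence.

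A reader might infer that every visit-duration comparison, and cost per visit too, conditions on visit count. The text does not support that. The Welch test and ANOVA state no such covariate. Cost per visit is a ratio compared by simple t-test, beside overall OOP cost. Its weakness is a denominator that can differ by arm and a value undefined at zero visits. The figures above do not measure that weakness.

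**Conclusion.** The concern holds for one analysis: the visit-duration regression, on the reading that total visit count means the month-12 count. Its arm coefficient can be biased for the randomised effect on duration. It need not be: the bias vanishes if the arms' counts do not differ, or if nothing links count and duration.

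Under the assumed model, the size runs from negligible (about 5 to 6% false positives at a loading of 0.2) to material (up to −0.20 SD and 33% at a loading of 0.5 with a shift of 0.8 SD). These figures illustrate; they do not predict what the trial will show.

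A reader might go further and doubt the trial's main result. Nothing here bears on it: the primary EASI analysis does not use visit count, and neither do the OOP cost analyses as written. This is a defect in a secondary analysis that is worth correcting because the correction is easy.

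**What to change.** 1. Remove the post-randomisation visit count from the visit-duration regression. Adjust instead for age group and site, which section 9.3.1 already requires in all models, and for baseline CSI visit count and duration. If the baseline count was meant all along, say so.
2. Name this model, or the unadjusted comparison, as the main duration analysis. Label any model adjusted for the month-12 count exploratory, and state that its coefficient is not the randomised effect.
3. State how patients with no visits enter mean duration and cost per visit, including those with no visits at baseline, who have no baseline duration to adjust for.
4. Make the already planned comparison of overall OOP cost per patient, zeros included, the main cost comparison. Report cost per visit descriptively, beside the visit counts.

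The cost is a change of wording in section 9.3.3. It needs no new data, visits or patients.

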1 PROTOCOL SUMMARY

1.1 SYNOPSIS

Title:	Team-Based Connected Health to Improve Clinical Outcomes and Access in Atopic Dermatitis
Study Description:	This is a pragmatic, randomized, controlled, equivalency trial. This 12- month trial will evaluate the impact of an online, team-based connected health (TCH) model for management of atopic dermatitis (AD) as compared to in-person care. 300 patients will be randomly assigned to the online TCH model or the in-person control arm stratified by two factors: age (<18 years vs. 18+ years) and study site. This pragmatic, randomized trial will compare AD disease severity (Aim 1), quality-of-life and access-to- care measures (Aim 2), and costs (Aim 3) between the two models.
Objectives:	The primary goal of the protocol is to evaluate whether an online, team- based connected (TCH) health model results in equivalent improvements in disease severity and quality of life, provides better access to specialist care, and is cost-saving compared to usual in-person care for AD management. We will perform a pragmatic randomized equivalency trial to compare the online, TCH model versus in-person care. The specific aims of the study are as follows:
	Primary Objective (Aim 1) : Compare differences in AD severity, as measured by the Eczema Area and Severity Index (EASI), Patient-Oriented Eczema Measure (POEM), and validated Investigator Global Assessment (vIGA), between patients randomized to Team-Based Connected Health and in-person care in a 12-month pragmatic, randomized equivalency trial.

Endpoints:	Secondary Objectives (Aim 2): Compare differences in quality of life as measured by dermatology-specific instruments (Dermatology Life Quality Index / Children's Dermatology Life Quality Index) and a generic instrument (European Quality of Life-5 Dimensions) between patients randomized to Team-Based Connected Health and in-person care. Furthermore, we will compare differences in access-to-care measures such as transportation and time needed for evaluation between patients randomized to Team-Based Connected Health and in-person care. Secondary Objectives (Aim 3): Compare differences in healthcare costs from a societal perspective between Team-Based Connected Health and in-person care through cost-minimization analysis. The primary and secondary endpoints are as follows: Primary Endpoint :			
	• Change in EASI from baseline averaged across 12 months.			

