4 STUDY DESIGN

4.1 OVERALL DESIGN

This study is testing the hypothesis that team-based connected health (TCH) model results in equivalent improvements in disease severity and quality of life, provides better access to specialist care, and is cost-saving as compared to usual in-person care for management of patients with atopic dermatitis (AD).

This is a 12-month, pragmatic, randomized, controlled, equivalency trial to evaluate the impact of an online, team-based connected health (TCH) model for management of atopic dermatitis (AD) as compared to in-person care. A total of 300 participants will be randomly assigned to the online TCH model or the in-person control arm.

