9.3 STATISTICAL ANALYSES

9.3.1 GENERAL APPROACH

For this pragmatic, randomized trial, we will compare patients randomized to the online, team-based connected health (TCH) versus patients receiving in-person care across one year. The overall analytical strategy is to use linear mixed or generalized estimating equations, depending on the outcome variable, to account for repeated measures within patients. Random effects for patients will be included in the model so that the estimates of any patient-level variables will be appropriately calculated. Additionally, we will adjust *a priori* for the randomization stratification factors site and age group (<18 years, and 18+ years) in all models. While we do not anticipate a site-level main effect, random effects for site will be included in the model in case there are factors common to patients within a site that affect the outcome.

For comparison of AD disease severity (Aim 1) and quality of life (Aim 2), we will test an equivalence hypothesis between the interventions using longitudinal linear mixed effects modeling; this allows for the estimation of intra-individual variance. Using this same technique, we will test the hypothesis of improved access to specialist care (Aim 2) and cost-saving (Aim 3) with the TCH model compared to the in- person model.

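### No single test decides the cost-saving hypothesis, and costs may be transformed at discretion with no return to mean cost, so a saving can be declared when mean costs are equal

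*Combined protocol and SAP*

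**What the plan says.** Section 4.1 makes cost-saving part of the trial's hypothesis. The synopsis (section 1.1) describes Aim 3 as follows: "Compare differences in healthcare costs from a societal perspective between Team-Based Connected Health and in-person care through cost-minimization analysis".

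Two sections then say how cost-saving will be tested, and they differ.

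- Section 9.3.1, directly after introducing longitudinal linear mixed effects models: "Using this same technique, we will test the hypothesis of improved access to specialist care (Aim 2) and cost-saving (Aim 3".
- Section 9.3.3, Analysis of Costs: "Out-of-pocket (OOP) costs will be evaluated using a combination of t-tests, ANOVA, least squares regression, and random-effects gamma regression".

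Section 9.3.3 sets an order. It begins with two outcomes: "Initial analyses will compare total OOP costs per visit and overall OOP costs between the two treatment groups using simple t-tests". Multiple linear regression of total OOP cost comes next, "adjusting for relevant covariates such as treatment site, age, sex, baseline EASI score, and history of asthma". Gamma regression follows and is labelled a sensitivity analysis. No other method is given a role. The section then allows a change of scale, "Given that cost data often exhibit a skewed distribution, appropriate transformations or robust estimation methods will be applied where necessary to improve model fit", and closes with one threshold: "Statistical significance for all analyses will be set at p<0.05". It states neither sidedness nor a multiplicity rule for the cost tests.

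**The concern.** A cost-minimization analysis asks which arm costs less on average, in money. That is a difference in arithmetic means. A test on log cost compares geometric means, and other transformations likewise compare something other than mean cost. If the two arms differ in the spread of costs, geometric means can differ while arithmetic means are equal.

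Section 9.3.3 leaves the decision to transform until model fit has been seen, and plans no step back to mean cost. It also leaves open which outcome (overall or per visit) and which method settles the hypothesis. The mixed model in section 9.3.1 adds another candidate and does not resolve the choice. At stake is whether a reported saving reflects mean cost or the scale and method chosen.

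**Working it through.** **Inputs from the documents.** Randomisation is 1:1 with 300 patients (sections 5.4.1 and 9.1), so 150 per arm. With the 15% attrition in section 9.1, 300 x 0.85 / 2 = 127.5, taken as 127 per arm. The threshold is p<0.05, read as two-sided because no side is stated. The documents give no mean, SD, distribution or power figure for costs, so there is no cost figure of the plan's own to reproduce.

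**Assumptions.** Costs are lognormal with no zeros, and log-SDs run from 1.0 to 1.5. These values are illustrative.

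**Step 1: change of scale with equal mean costs.** The mean of a lognormal variable is exp(m + s²/2). Equal arithmetic means (0 = in-person, 1 = TCH) therefore imply

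d = m1 - m0 = (s0² - s1²)/2, geometric-mean ratio = exp(d), SE = sqrt((s0² + s1²)/n),

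P(significant, favouring TCH) = Φ(-d/SE - 1.96).

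With n = 127 per arm:

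| Log-SD in-person / TCH | d | Geometric-mean ratio | SE | False saving |
|---|---|---|---|---|
| 1.0 / 1.0 | 0 | 1.00 | 0.125 | 2.5% |
| 1.0 / 1.1 | -0.105 | 0.90 | 0.132 | 12.2% |
| 1.0 / 1.2 | -0.220 | 0.80 | 0.139 | 35.5% |
| 1.0 / 1.3 | -0.345 | 0.71 | 0.146 | 65.9% |

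For example, at 1.0 / 1.2: d = (1.00 - 1.44)/2 = -0.22, SE = sqrt(2.44/127) = 0.139, and Φ(1.587 - 1.96) = Φ(-0.373), about 0.355. Simulation of 4,000 trials at this setting gave 36.6%.

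Section 9.3.3 also copies baseline CSI values forward for patients without month-12 data, so the analysed number could be nearer 150 per arm. At 150 the same formula gives 40.7% (1.2) and 73.1% (1.3).

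If the spread is reversed (1.2 in-person, 1.0 under TCH), d changes sign. The 35.5% becomes a false extra cost, and a false saving is almost never seen: Φ(-1.587 - 1.96) = Φ(-3.547).

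**Step 2: the untransformed test under the same conditions.** The simulated unadjusted t-test on total cost declared a false saving in 2.2% (1.0 / 1.0), 3.9% (1.0 / 1.2) and 7.5% (1.0 / 1.5) of trials at 127 per arm, and in 2.2%, 3.1% and 8.0% at 150 per arm. Nominal is 2.5%.

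**Step 3: several tests, no true effect.** Both arms have the same cost distribution (log-SD 1.0), with 127 per arm, 4,000 trials and visit counts of 1 plus a Poisson variable with mean 3 (assumed).

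| Tests considered | Any p<0.05, either direction | Any false saving |
|---|---|---|
| t-test on total, t-test per visit, adjusted linear regression | 7.8% | 3.9% |
| plus gamma regression | 9.5% | 4.5% |
| plus log-scale versions | 13.0% | 6.2% |

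At 150 per arm the either-direction figures are 8.8%, 10.6% and 14.7%. The tests are strongly correlated; four independent tests would give 1 - 0.95^4 = 18.5%. A one-way ANOVA of two arms is the pooled t-test (F = t²), so it adds no further error and no further information.

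**The case against.** The plan is more ordered than a bare list of methods suggests. The t-tests come first and regression second, apparently on untransformed cost, and gamma regression is already a sensitivity analysis. It would be wrong to count gamma as a planned deciding test. That order still does not say which result settles the hypothesis.

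A reader might infer that the plan commits to a log-scale test. It does not. Section 9.3.3 speaks of transformations or robust methods and never mentions logs. The log reading is an inference from the reference attached to that sentence (reference 32), whose title concerns logged outcomes, unequal variance and retransformation. The authors thus point to the hazard themselves, but they specify no step to deal with it.

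A reader might also infer that the plan is tilted towards TCH. The documents do not support that. The false saving needs wider log-scale spread under TCH; equal spread keeps the test at its level and the opposite pattern reverses the error. No cost data are given to say which holds.

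Nor do the documents exclude baseline OOP cost. The covariate list is open-ended, and a mixed model as in section 9.3.1 would use the baseline value as a repeated measure. What stands is that the five named covariates omit it and the choice is left open.

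Tests of visit counts and durations should not be added to the error rate for cost-saving, because section 3 lists utilization and costs as separate endpoints.

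Finally, the untransformed t-test is not immune: it drifts to about 8% false savings at log-SD 1.0 versus 1.5. That stands as a limit on the remedy.

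**Conclusion.** The point holds. The plan names no deciding outcome, test or scale for cost-saving, its two statistical sections assign different methods, and a discretionary transformation is allowed with no return to mean cost. Following it as written could produce a wrong conclusion about mean cost.

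The change of scale is the larger problem. With equal mean costs and 127 per arm, false savings rise from 2.5% with equal spread to about 12%, 36% and 66% as the TCH log-SD goes to 1.1, 1.2 and 1.3 against 1.0 in-person. The choice among tests adds moderate inflation: roughly 8-13% in either direction, about half of it false savings. All these figures rest on assumed lognormal costs without zeros; they show what can happen and do not forecast this trial.

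Separately, section 9.3.3 analyses OOP cost whereas the synopsis promises a societal perspective, so even a sound OOP result would not establish the saving described there.

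Aim 3 is secondary, and nothing here touches the primary EASI comparison. The correction should be made before the cost data are analysed.

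**What to change.** 1. Name one deciding test: the difference in arithmetic mean total OOP cost per randomised patient, untransformed, with stated sidedness, by linear regression on arm, site, age group and baseline OOP cost from the CSI, with a bootstrap or robust confidence interval.
2. Label the unadjusted t-tests and per-visit cost as sensitivity analyses alongside gamma regression, and drop the ANOVA that repeats the t-test.
3. Delete the transformation clause, or require any transformed model to be returned to mean cost in a way that allows for unequal variance between arms.
4. Reconcile section 9.3.1 with section 9.3.3 on the method for cost-saving.
5. State that an OOP result supports an OOP saving only, not the societal-perspective saving in the synopsis.

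The baseline covariate needs no new data, since the CSI is already collected at baseline. If baseline and month-12 costs correlate at 0.3 to 0.7 (an assumption; the documents give no value), residual variance falls by r², that is 9% to 49%. Copying baseline values forward for missing patients is a separate matter that this change does not cure: with 15% copied, an effect of 20 would be estimated as about 0.85 x 20 = 17.

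The cost is wording only. The plan loses the freedom to choose a model after seeing the data. Under extreme skew the mean-scale test can still drift, which is the reason for the bootstrap or robust interval; how far either removes the drift was not calculated.
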